**Effectiveness of additional thoracic paravertebral block in
improving anesthetic effects of regional anesthesia for
proximal humeral fracture surgery in elderly patients**

Study Protocol

2019.3.21

Principle Investigator: [name]

Co-Investigator: [name]

[name]

[name]

[name]

[name]

[name], PhD

[name], PhD

Objective

To investigate whether supplementary T2 thoracic paravertebral block (TPVB) could improve the anesthetic effect of cervical-brachial plexus block based regional block.

Background

Proximal humeral fractures (PHF) is a common disease occurring in the elderly population over 60 years. The deltopectoral approach is commonly used in the PHF surgery. The innervation of PHF surgical area is complicated and unclear. Ultrasound-guided brachial plexus combined with cervical plexus block is probably inadequate for the anesthesia of proximal humeral surgery. Missing blockade of T1-T2 nerves may be the reason. The primary aim of this trial is to investigate the effectiveness of additional T2 thoracic paravertebral block (TPVB) in improving the anesthetic effects of regional anesthesia for elderly patients in proximal humeral fracture surgery.

Methods

We have designed a two-armed, parallel, randomized controlled trial (RCT) to observe the anesthetic effects of ultrasound-guided brachial and cervical plexus block with or without additional T2 TPVB in terms of the following outcomes: success rate, sensory block and safety. The elderly patients aged 65 or older, referred for anterior approach proximal humeral fracture surgery, will be enrolled. Each participant will be randomly assigned 1:1 to receive IC block (combined interscalene brachial plexus with superficial cervical plexus block) or ICTP block (combined thoracic paravertebral block with IC block). The primary outcome is the success rate of surgical anesthesia. The secondary outcomes are as follows: sensory block at surgical area, proportion of participants who need supplementary anesthesia (intravenous remifentanyl or conversion to general anesthesia), cumulative doses of intraoperative vasoactive medications and adverse events. The necessary sample size is estimated to be 80.

Randomization and blinding

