Random allocation will be performed by a researcher (HZ) before the trial using a randomization sequence. The allocation concealment strategy is achieved with sequentially numbered, opaque, sealed envelopes to conceal the sequence until the intervention is assigned. The envelopes will be opened sequentially before the nerve block is performed. Participants will be randomly assigned in a 1:1 ratio to receive IC block or ICTP block. As the nerve block intervention cannot be blinded from participants and staff implementing the intervention, only the outcome assessor and data statistician will be kept blinded to the randomized allocation and intervention. The envelope will be resealed after confirming the allocation.

Interventions

All the participants will undergo preoperative fasting for 8 hours and water deprivation for 2 hours. After placement of standard ASA monitors, intravenous access for fluid infusion will be established in the forearm. No sedatives or analgesic medication will be given prior to the block. The participant will receive ultrasound-guided IC block or ICTP block according to the allocation. It will be performed following standard skin disinfection with a SonoSite S-Nerve™ ultrasound machine (Bothell, WA, USA). The entire nerve block procedure of all the participants will be performed by the same anesthesiologist, who is skilled in performing ultrasound-guided regional anesthesia.

In the IC group, the procedure will be performed as followed.

The participant will be placed in the lateral decubitus position with the operative side upwards. A linear array transducer (6-13 MHz) with a sterile cover and a 22G (gauge) block needle will be used. An in-plane approach, advancing the needle along the longitudinal axis of the transducer and visualizing the entire shaft, will be employed. Twenty ml of 0.375% ropivacaine will be injected between superior and middle trunk of brachial plexus at C7 level to reduce phrenic nerve palsy. The transducer will be then moved cephalad until the superficial cervical plexus emerges from the C4 intervertebral foramen. Ten ml of 0.25% ropivacaine will be injected to block the nerve.

In the ICTP group, the procedure will be performed as followed.

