On the basis of IC block, T2 TPVB will then be performed. The T2-T3 intervertebral space should be determined by ultrasound image scanning and palpation counting from C7 spinous process. A curve array transducer (2-5 MHz) will be placed at the T2-T3 intercostal level with a slightly oblique scan to visualize the transverse process, costotransverse ligament, internal intercostal membrane and parietal pleura. A 10cm, 22G needle will be introduced into the thoracic paravertebral space beyond the internal intercostal membrane with its tip positioned outside the transverse process. Following negative aspiration of air, blood or cerebrospinal fluid in the needle, 10 ml of 0.25% ropivacaine will be injected into the paravertebral space.

Then the participant will be placed in the supine position. Twenty minutes later, after the sensory block assessed, the participant will be transferred to the operating room and placed in a beach-chair position. One mg midazolam will be given intravenously. Oxygen will be routinely given via a nasal catheter at the flow rate of 3L/min until the end of operation. In case of inadequate analgesia, remifentanil (50 μ g/ml), propofol (10mg/ml) and laryngeal mask airway (LMA) insertion will be prepared. The anesthetic effects will be assessed since the operation begin: 1) if it is successful, the operation will be continued; 2) if it is failed, the operation will be paused and remifentanil will be given intravenous at the rate of 0.25 μ g/kg/min. Two minutes later, the operation will be continued if the participant is satisfied with the anesthetic effect. The rate of intravenous remifentanil can be appropriately regulated (no more than 0.25 μ g/kg/min) in the following operation according to the P_{ET}CO₂ and respiratory rate of the participant. On the contrary, the intolerable participant will be induced with propofol (1.5-2 mg/kg) for converting to GA with LMA. The participant who received GA will be transferred to post-anesthesia care unit (PACU) after the operation.

Statistical analysis plan

Primary analyses will be undertaken on an intention-to-treat basis, including all participants as randomized, except those who withdraw consent for the use of their

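### Does timing the sensory test from the last block give the ICTP arm an unfair head start?

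*Combined protocol and SAP*

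**What the plan says.** Under Interventions, both arms receive the same IC block. Its last step is the cervical plexus injection: "Ten ml of 0.25% ropivacaine will be injected to block the nerve". In ICTP a further block follows: "On the basis of IC block, T2 TPVB will then be performed". That block needs its own level finding and a change of probe ("A curve array transducer (2-5 MHz) will be placed at the T2-T3 intercostal level with a slightly oblique scan"), then needle placement, aspiration and injection. The text after the ICTP description appears to apply to both arms: "Then the participant will be placed in the supine position. Twenty minutes later, after the sensory block assessed". Transfer to the operating room comes next. No duration is given for the TPVB, and the IC arm has no sham block or matched wait.

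Under Methods, the secondary outcomes include "sensory block at surgical area, proportion of participants who need supplementary anesthesia". The primary outcome is the success rate of surgical anesthesia, which Interventions has assessed from the start of the operation. Which territories are tested, how they are scored and whether they are pooled is not stated. Background gives the hypothesis: "Missing blockade of T1-T2 nerves may be the reason". Under Randomization and blinding, "only the outcome assessor and data statistician will be kept blinded to the randomized allocation and intervention".

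**The concern.** The aim is to learn what TPVB adds to the IC block, so the IC block should otherwise be on the same footing in both arms. If the 20 minutes run from supine positioning after the last injection, the IC block has had longer to work in ICTP when sensation is tested. Sensory block normally only increases over this window, so the extra time is neutral or favours ICTP. The usual safeguards do not remove it. Randomization balances patients, not schedules. Blinding the assessor prevents slanted scoring but not a true difference in block age. Nor does having one operator ("The entire nerve block procedure of all the participants will be performed by the same anesthesiologist") shorten the TPVB to nothing.

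At stake is the reading of one secondary outcome. A difference in IC-supplied territories, or in a score that pools them with T2, could be credited to TPVB when part of it is only a longer wait.

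**Working it through.** **Inputs from the documents.** The IC block precedes TPVB, the wait is 20 minutes after supine positioning, the total sample is 80 at 1:1 (40 per arm), categorical data are tested by chi-square or Fisher's exact test, and the significance level is 0.05. The documents give no figure for this timing effect, so there is none to reproduce.

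**Inputs that must be assumed.** The TPVB time d (5 or 10 minutes here) and the onset curve F(t), the probability that an IC-supplied territory is blocked t minutes after the IC block.

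**Formula.** With no true TPVB effect in that territory, the gap is F(20 + d) − F(20). Two curves with the same median m are compared:

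- exponential: F(t) = 1 − 2^(−t/m)
- log-normal, sigma 0.5: F(t) = Φ(ln(t/m)/0.5)

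Example, exponential with m = 10: F(20) = 1 − 2^(−2) = 0.750, F(25) = 1 − 2^(−2.5) = 0.823 and F(30) = 1 − 2^(−3) = 0.875. The gaps are 7.3 and 12.5 points.

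| Median onset (min) | Exponential: gap in points, d = 5 / 10 | Exponential: chance of a significant result favouring ICTP | Log-normal: gap in points, d = 5 / 10 | Log-normal: same chance |
|---|---|---|---|---|
| 5 | 3.1 / 4.7 | 1.2% / 2.1% | 0.2 / 0.3 | about 0% |
| 7 | 5.4 / 8.7 | 5.7% / 13.5% | 1.2 / 1.6 | about 0% |
| 10 | 7.3 / 12.5 | 8.1% / 22.1% | 4.9 / 6.9 | 3.5% / 6.8% |
| 15 | 8.2 / 14.7 | 7.6% / 21.3% | 12.9 / 20.0 | 21% / 57% |
| 20 | 8.0 / 14.6 | 7.7% / 20.4% | 17.2 / 29.1 | 28% / 72% |

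The chances are exact enumerations of a two-sided Fisher test at 0.05 with 40 per arm. The nominal value in this one direction is 2.5%. Chi-square gives higher figures, for example 12.3% and 30.3% for the exponential curve at median 10.

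**What the table shows.** The direction never changes, but the size does. At a median of 7 minutes the exponential curve suggests a modest inflation and the log-normal curve none. The large values, at medians of 15 to 20, need 28% to 50% of IC-supplied territories (log-normal; 40% to 50% exponential) to be still unblocked at the planned test, shortly before transfer to surgery. Nothing in the documents suggests so slow a block, though nothing excludes it.

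**T2 territory.** The IC block is not aimed at T2, and the 20 minutes run from the end of the TPVB. A separate T2 result therefore gets no head start from the age of the IC block.

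**Primary outcome.** Assume a further 30 minutes from test to incision, so that the IC block is 50 minutes old in IC and 55 or 60 in ICTP. At median 10 the exponential gap is 2^(−5) − 2^(−5.5) = 0.9 points, or 2^(−5) − 2^(−6) = 1.6 points. At the slowest median, 20, it is 2.8 or 5.2 points. The log-normal values are smaller: under 0.1 points at median 10 and 1.2 or 1.9 at median 20.

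**The case for a change.** The strongest case for acting is that the lag is built into one arm, has a known direction and cannot be undone by blinding or randomization. The Objective asks what TPVB adds, and the plan neither rules out a pooled score nor provides for the time records that would show whether IC onset was complete. Testing both arms at the same time since the end of the cervical plexus injection would bring the gap in shared territories to zero under either curve. Recording times and reporting by territory would cost almost nothing.

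The mechanism and its direction stand. The case for a change does not, for three reasons.

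- **The common clock is a trade-off.** The protocol ties transfer to the sensory assessment. A later test in the IC arm therefore means later surgery and an older IC block when the primary outcome is judged. It would alter the control strategy for the main comparison to tidy one secondary outcome.
- **The plan states no rule that gives a wrong answer.** Methods compares IC block with and without TPVB as whole procedures, and in that comparison the minutes spent on TPVB belong to ICTP. Misattribution arises only if someone credits IC-territory differences to TPVB, and the plan does not say that anyone will.
- **The wording is loose.** The 20 minutes may attach to the transfer, with the test at some unstated point before it. Block age would still be unequal, but the figures based on 20 against 25 or 30 minutes would lose their footing.

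Time records and separate reporting remain good practice. They fill in detail for an outcome that the plan describes only briefly, and do not correct an error.

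**Conclusion.** No change is needed. On the natural reading, the shared block is older at the sensory test in ICTP by an unstated number of minutes. In IC-supplied territories this can only be neutral or favour ICTP. For lags of 5 to 10 minutes the assumed gap runs from 0.2 points (median 5, log-normal) to 12.5 points (median 10, exponential). It is larger only if a good share of the IC block is still developing when the patient is about to go to surgery. All of these figures rest on assumed lags and onset curves, so the documents support the direction but no particular size.

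The hypothesis of missing T1-T2 blockade can still be tested in its own territory. The primary outcome is affected by 0.9 to 1.6 points at most at median 10, under the assumed 30 minutes from test to incision. Removing the remaining imbalance would disturb the control arm before the primary assessment. Analysts can deal with it sensibly by showing IC-supplied and T2 territories separately and reading differences in the former with caution.
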